A measure that is taken to eliminate an immediate hazard to a participant's health or safety. Significant safety issues where an urgent safety measure is required to be taken to eliminate an immediate hazard must be classified as a significant safety issue requiring an urgent safety measure. The Principle

Investigator must be notified of any significant safety issues that meet the definition of an urgent safety measure should be notified within 72 hours.

Examples include:

- a serious adverse event that could be associated with the trial procedures and that requires modification of the conduct of the trial.
- a patient population hazard, such as lack of efficacy of an intervention used for the treatment of a life-threatening disease.

USM reports must be recorded in the [Myo Munchee Protocol 0001 Safety Monitoring Register](#).

8. Safety Assessment Flow Chart Investigational Medical Device Trials

[figure not shown]

Image. Flow chart from UNSW Clinical Trial Protocol Template.

9. Register of Clinical Trial Safety Monitoring Reports

A register of all event reports assessed and classified is to be retained by the Principal Investigator.

10. Reporting of Clinical Trial Safety Monitoring Reports

Single case reports of Adverse Events Adverse Reactions, Serious Adverse Events (SAEs), Serious Adverse Reactions (SARs), reports do not need to be reported to the IRB. All single case reports must be recorded in a safety monitoring register.

11. Emerging Safety Issues

If safety concerns are identified, the principle investigator and involved staff members will establish a plan to minimize the time participants may be placed at excess risk of harm.

12. Non-compliance, Protocol Deviation and Serious Breaches of Good Clinical Practice

Protocol Deviation

A protocol deviation is defined as any breach, divergence or departure from the requirements of Good Clinical Practice, the clinical trial protocol, the clinical trial standard operating procedures, or the human ethics approval that does not have a significant impact on the continued safety or rights of participants or the reliability and robustness of the data generated in the research or clinical trial. Protocol deviations are events that do not occur persistently or systematically and do not potentially result in participant harm. Examples of protocol deviations include but are not limited to:

- Deviations because of participant adherence to the protocol, including rescheduled study visits, participants refusal to complete scheduled research activities or failure to complete self-report questionnaires required by the study protocol.
- The completion of consent forms, safety monitoring report, case report forms or data collection tools in a manner that is not consistent with the protocol instructions or failure to make reports within the required reporting timeframes.
- Administration of the clinical trial investigational medical product or device in a manner that is not consistent with the manufacturer's instructions for use.
- Use of an unapproved version of the participant information statement or recruitment of participants using unapproved recruitment procedures.
- Inclusion of a participant that does not meet the inclusion criteria.
- An urgent safety measure must be taken to eliminate an immediate hazard to a participant's health or safety.

Serious Breach of Good Clinical Practice

A serious breach is defined as a breach of Good Clinical Practice, the clinical trial protocol, the clinical trial standard operating procedures, or the human ethics approval that is likely to affect to a significant degree the safety or rights of participants or the reliability and robustness of the data generated in the clinical trial. Examples of serious breaches include but are not limited to:

- Persistent or systematic non-compliance with the instructions for completing consent forms, safety monitoring forms, case report forms or data collection tools that result in continued missed or incomplete data collection.
- Failure to record or report adverse events, serious adverse events, suspected unexpected serious adverse reactions, significant safety issues where urgent safety measures were implemented.
- Failure to conduct clinical trial procedures following the clinical trial delegation log.
- Widespread and uncontrolled use of protocol waivers affecting eligibility criteria, which leads to harm to trial subjects.
- Failure to report investigational medical product or device defects to the clinical trial sponsor or any relevant regulatory body.
- Failure to conduct research following the issued approvals, permits or licenses by required laws, regulations, disciplinary standards relating to the responsible or safe conduct of research.
- Concealing or facilitating breaches (or potential breaches) of the Research Code by others.
- Researching without the requisite approvals, permits or licenses required by laws, regulations, and disciplinary standards related to the responsible or safe conduct of research.
- Failure to conduct research as approved by an ethics review body where that conduct leads to (or has the potential to) results in participant harms.
- Any breaches as outlined in the US National Science Foundation Responsible and Ethical Conduct of Research conduct of research that leads to (or has the potential to) result in participant harms.

14. Reporting Protocol Deviations

- Protocol deviations occurring at a site must be documented in site files and reported to the Principal Investigator.
- The Principal Investigator must review the protocol deviation and the clinical trial protocol to establish the corrective actions and preventative steps to prevent the deviation from reoccurring.

15. Reporting of a Serious Breach

- A serious breach occurring at a participating site must be reported to the Principal Investigator within 72 hours.
- The Principal Investigator must review the serious breach, along with the clinical trial protocol, to develop a Corrective and Preventive Action (CAPA) that defines the steps to prevent the serious breach from reoccurring.

16. Review of a Protocol Deviation and a Serious Breach

- The Principle Investigator will review reports to establish whether the event meets the definition of a protocol deviation or serious breach, to establish whether the

proposed is appropriate and establish whether there is or will be an ongoing impact on the reliability and robustness of the data generated.

- Principle Investigator and Myo Munchee will seek advice from the approving IRB on the corrective and preventive action

Data Management and Software

Deidentification of data

1. Refer to this document for patient enrollment information - [link](#)
2. Patients will be assigned a code upon enrollment so that their information is de identified across all systems except for the clinics that they are receiving care
3. Case ID example: Ben Cook
 - a. First subject enrolled in the study: 01
 - b. First name: Ben
 - c. First 2 letters of last name: CO
 - d. Case ID: 01CO

Data Management

Patient data storage and disposal

- Data storage will be managed by Myo Munchee, SleepInventory.com a service of Child Uplift, Inc., and the Children's Airway Screen Taskforce (CGASP database)
- Storage of patient data will be for 15 years from the date the patient consents to be part of the study
- The data will be stored in the USA and Australia

Data safety, security and confidentiality

- Data will be de-identified by the treating practitioner and team in the clinic that the patient attends. Name and address will not be entered into the study database but will be entered into the clinics database. Instead, a patient identification number and month and year of birth will be assigned to the patient and entered into the database along with the email address that the parent enters for online questionnaire completion.

Data access

- The de-identified data will be accessible to the principle investigator and the study coordinator throughout the whole study and the biostatistician at the studies completion.
- The identified data will be stored and accessed by the treating clinicians throughout the duration of the study and while the patient is under their professional care.
- A user logbook of start and stop dates of data access will be maintained
- Data will be hosted in the USA and Australia

Data retention and publication

- Data will be retained for up to 15 years and will be used for journal publication, and presentation purposes

Data reviewing, validation and rectification

- Throughout the study, the data will be reviewed every month
- The data will be reviewed for quality purposes to ensure that accurate and correct information has been added to the database
- There will be inbuilt validation checks in the survey and clinical measurements form that the patients parent and treating clinician complete. This will assist in the user entering the correct data
- If there is clinical information missing, input incorrectly, or a mistake made by the treating clinician, this will be addressed and rectified to ensure that the correct information has been added to the database
- If a survey is incomplete or not attempted altogether. Within 1 week of the survey being sent out the parent will receive a reminder, however, after 1 week they will not receive a reminder and the information will be considered incomplete or missing

Data monitoring

- Independent data monitoring may be required if there are challenges confirming the database record discrepancies between the clinical records and the centralized database used for the study

Software - Patient data collection and storage

- Microsoft OneDrive
- Microsoft Excel
- Microsoft Forms
- Sleep inventory - <https://www.sleepinventory.com/>
- Children's Airway Screening Taskforce

Patient Recruitment

Patient recruitment process

Refer to Appendix for detailed description

Marketing and advertising materials for recruitment

Informational A4 letters for each individual practice have been developed so patients can read and understand what is required to participate in the study. Refer to Appendix for an example.

Financial Information

Compensation to patients for Participation

The compensation associated with participating in the study will be broken into treatment groups.

1. Myo Munchee only group

- a. Free Myo Munchee device
- b. Follow up measurement appointments at T10 and T26: covered by Myo Munchee
- c. Treatment appointments: all 15-minute appointments covered by Myo Munchee
- d. \$250USD voucher if fulfill these criteria:
 - i. Attend all measurement appointments (3 total)
 - ii. Complete all monthly compliance logbooks (6 total)
 - iii. Attend minimum 6 out of 7 of the 15-minute treatment appointments (7 appointments)

2. OMT only group

- a. \$250USD voucher if fulfill these criteria:
 - i. Attend all measurement appointments (3 total)
 - ii. Complete all monthly compliance logbooks (6 total)
 - iii. Attend minimum 6 out of 7 of the 30-minute treatment appointments (7 appointments)

3. Myo Munchee and OMT group

- a. Free Myo Munchee device
- b. \$250USD voucher if fulfill these criteria:
 - i. Attend all measurement appointments (3 total)
 - ii. Complete all monthly compliance logbooks (6 total)
 - iii. Attend minimum 6 out of 7 of the 30-minute treatment appointments (7 appointments)

4. Control group

- a. Free Myo Munchee device at end of study
- b. \$250USD voucher if fulfill these criteria:
 - i. Attend all measurement appointments (3 total)

The \$250 USD voucher that can be spent at one or split across multiple practices

Costs for Participation

The costs associated with participating in the study will be broken into the treatment groups and to the specific appointments below:

1. Myo Munchee only group

- a. Measurement appointments:
 - i. Initial appointment: billed to patient's insurance provider as an initial evaluation consultation

2. OMT only group

- a. Initial and follow up measurement appointments: billed to patient's insurance provider as an initial evaluation consultation

- b. All treatment appointments: billed to patient's insurance provider as OMT has established therapeutic benefit
3. Myo Munchee and OMT group
 - a. Initial and follow up measurement appointments: billed to patient's insurance provider as an initial evaluation consultation
 - b. All treatment appointments: billed to patient's insurance provider as OMT and Myo Munchee has established therapeutic benefit
4. Control group
 - a. No cost

Ethics

- To be submitted to Allendale Investigational Review Board - <https://www.allendaleirb.com/>
- Email: [contact]
- <https://www.wma.net/policies-post/wma-declaration-of-helsinki-ethical-principles-for-medical-research-involving-human-subjects>

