To evaluate the effectiveness of three different treatment options, either as sole interventions, or as adjunctive intervention strategies, for mitigating symptoms often associated with SM, OMD, SDB and/or TOT phenotypes when initially detected under the age of 72 months old.

Outcomes and objectives

For each child enrolled in the study, the outcomes below are desired.

- 1. Primary outcomes**
 1. Palatal transverse width expansion
 2. Palatal sagittal depth expansion
 3. Palatal vault height expansion
- 2. Secondary outcomes**
 1. OMD resolution
 2. Improvement in sleep and behavior
- 3. Study objectives are intended for the practitioner community**

Eligibility Criteria, Materials and Methods

Eligibility criteria

Inclusion Selection Criteria:

1. Aged between 36 - 60 (3-5 yrs) months old and will not turn 6 years of age before the study completion
2. Diagnosed with having at **least two** maxillary skeletal-dental malocclusion traits as determined by the measurements below
 - a. Palatal transverse (width), detailed measurement information described in methods section
 - i. Anterior inter-canine width (Thilander study [link](#))
 1. Male: age range (4.7-5.55 years); range 26.8-32.8mm, average = 30.5mm. If patient is below 26.8mm, eligible for study
 2. Female: age range (4.6 - 5.2 years); range 25.6-32.3mm, average = 28.4mm. If patient below 25.6mm, eligible for study
 - ii. Posterior inter-molar width (Bogue index, 24mm + age) measurement for both male and female
 1. 3-year-old: and less than 27mm (posterior)
 2. 4-year-old: and less than 28mm (posterior)
 3. 5-year-old: and less than 29mm (posterior)
 - b. Palatal sagittal depth/length (Thilander study [link](#))
 - i. Second deciduous molar (from distal alveolar crest to incisive papilla):

1. Male: age range (4.7-5.55 years); range 22.0-28.5mm, average = 25.1mm. If patient below 22mm, then eligible for study.
2. Female: age range (4.6 - 5.2 years); range 18.0-25.0mm, average = 21.4mm. If patient below 18.0mm, eligible for study.
- c. Palatal vault height (Thilander study [link](#))
 - i. Second deciduous inter-molar height (measured from the center of the line connecting the disto-gingival margins of the 2nd molars (at alveolar crests) down to the contact with the mid-palatal suture):
 1. Male: age range (4.7-5.55 years); height range: 12.5-17.0mm, average = 14.2mm. If patient below 12.5mm, eligible for study

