 2. Female: age range (4.6 - 5.2 years); height range: 12.0-16.0mm, average = 14.1mm. If patient below 12.0mm, eligible for study.
3. At least **one of the** identified OMD traits detailed below:
 - a. Resting mouth posture ([reference](#))
 - i. Gently pull down the chin at rest and again look to see where the tongue is once the lips have opened. This is performed after movement, eating and while the patient is sitting. Video recording will be performed to corroborate finding. The other
 1. Lips open at rest
 2. Suspected mouth breathing during the day and night
 3. Tongue rests on the floor of the mouth
 - b. Oral-Motor Developmental Sequence: Biting, swallowing and chewing function
 - i. No adult chewing pattern, indicative of what's expected at 36 months. If patient doesn't meet the attached feeding criteria, then they are eligible to participate - [link](#)

Exclusion Selection Criteria

1. A patient must be considered healthy to be included in this study. Definition of healthy: the patient does not have ongoing treatment, medication or specialized assessments (more than routine follow up exams) with health care providers regarding a condition. If they have had treatment for a condition (e.g. treated by respiratory physician for acute asthma hospitalization), it must have been 12 months or more since their last appointment with a health provider related to that condition
 - a. Of particular consideration
 - i. Ongoing care from a sleep physician or respiratory physician
 - ii. Current use of CPAP, nasal sprays, sleeping or behavioral medication to treat diagnosed sleep disorder or behavioral disorder
 - iii. Adenectomy or tonsillectomy within last 12 months
2. Any previous or current tumors or traumas in the head, neck and jaw region
3. Patients with any known genetic or congenital conditions that impair oral motor muscle function, oral motor coordination, or speech articulation, such as but not limited to muscular dystrophy, cerebral palsy, will be excluded from the study.
 - a. Patients with any known syndromic conditions to affect oral motor function, including but not limited to syndromes that involve craniofacial anomalies, neuromuscular disorders, or developmental delays affecting oral motor muscle control, speech

articulation, or swallowing, such as Down Syndrome, Pierre Robin sequence, or Moebius syndrome.

4. Children that do not have their 2nd molars by 36 months of age
5. Overweight, Z-scores
 - a. BMI above 85th percentile (z score of 1)

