 - i. Boys: <https://www.cdc.gov/growthcharts/data/extended-bmi/BMI-Age-percentiles-BOYS-Z-Scores.pdf>
 - ii. Girls: <https://www.cdc.gov/growthcharts/data/extended-bmi/BMI-Age-percentiles-GIRLS-Z-Scores.pdf>
6. History of prescription for therapeutic gum chewing and/or use of edibles in treatment program
7. Previous tongue tie releases (frenuloplasty and frenectomy)
8. Any therapeutic oral device treatment
9. Previous or current treatment from any other dental, OMT or orthodontic provider
10. Gross neglect of patient's oral health and presence of dental caries
11. Grade 4 tonsils on Brodsky scale

Screening Criteria

1. Accepts Myo Munchee on first presentation
2. Tolerates initial examination including taking measurements
3. Agrees to not seek out other medical treatment for their dental or OMD issues
4. Insufficient nasal patency - proxy for enlarged adenoids - unable to complete the Rosenthal test by reaching 20 breaths through nose with mouth closed ([reference](#))

Materials

1. Myo Munchees
 - a. Mini: 1.5 years - 4 years
 - b. Junior: 4 - 8 years
2. OMT materials
 - a. Dusico Balloon
 - b. Tongue depressor
 - c. Veggie straw
3. Dental materials
 - a. iTero: <https://itero.com/en-AU>
 - b. Palatometer - image 3 - [link](#)
 - c. Caliper - <https://www.harborfreight.com/hand-tools/measuring-marking/calipers-micrometer/calipers.html>

Methods

Power Calculation

With n=12 subjects per group (1 control and 3 treatment groups), totaling 48 subjects overall, we will have at least 80% power to detect a LARGE¹ effect size (defined as mean difference relative to pooled standard deviation) of 1.2 or higher between any of the treatment groups and control group. With 6 subjects in the control group and 12 subjects in the treatment group, we will only have a power of 60% to detect an effect size of 1.2 or greater.

To have 80% power to detect a medium ($d=0.6$) effect size between any of the treatment groups and control, we would require n=45 subjects per group.

Method of treatment group allocation

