Subjects eligible for participation in the study will be randomized to either Myo Munchee only (Group A) or Oral Motor Therapy only (Group B) or Myo Munchee + Oral Motor Therapy (Group C) or Control (Group D). Permuted block randomization with block size = 12 will be carried out using the following shinyApps: <https://baker-biostats.shinyapps.io/pblockrand/>. The randomization list will be attached to the enrolment document and concealed from the investigators until patients are recruited.

Treatment Groups

Dual certified Speech Language Pathologist and Certified Orofacial Myologist for the treatment groups will see all 48 patients

Group	Patients
Group A: Myo Munchee ONLY	12
Group B: Oral Motor Therapy ONLY	12
Group C: Myo Munchee + Oral Motor Therapy	12
Group D: Control, no treatment	12
Total number of patients	48

Treatment Protocols

Myo Munchee treatment protocol

The patients in this treatment group will use the Myo Munchee. Due to patient and therapist appointment scheduling, treatment may need to be performed over a video/internet call. This will be documented in the

¹ Using Cohen's d threshold for effect size (Cohen, 1988), small effect size = 0.2, medium = 0.5, large > 0.8

appointment notes whether it was an online or video meeting. Practitioner will also assess the ability of the patient to chew the Myo Munchee during each appointment and will note this.

Parental and patient education: <https://drive.google.com/drive/folders/1gI8FREl1xU1-2jF6NQLFtHGfgMYGnyZ1>

Patient requirements: Mirror used for exercises. Body is either standing against the wall, upright and supported in a chair or lying on the floor to ensure aligned posture. All exercises are performed 6 days per week (6/7)

Myo Munchee treatment protocol:

1. 1-minute x2 per day, week 1
2. 2-minute x2 per day, week 2
3. 4-minute x2 per day, week 3
4. 5-minute x2 per day, week 4
5. 6-minute x2 per day, week 5 onwards till 6 months

Total time commitment for at-home exercises: 72 minutes per week

Total time at-home commitment for 6 months: 72 hours

Oral Motor Therapy Treatment Protocol

This treatment group involves performing the required Oral Motor Therapy exercises. Due to patient and therapist appointment scheduling, treatment may need to be performed over a video/internet call. This will be documented in the appointment notes whether it was an in-person or online/video appointment.

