Linear mixed model with random subject intercept will be used to compare treatment and control groups. Adjustments for demographic and clinical variables will be performed if necessary. The main statistical analysis will be performed using intention-to-treat (ITT) principle with a secondary per-protocol analysis. For the ITT analysis, all subjects with at least baseline measurements will be included, while for the per-protocol analysis, only subjects who did not deviate from the protocols will be included.

All statistical hypothesis testing will be performed using 5% significance level.

Measurements

Clinical Measurements

Dental Measurements

[Videos](#) demonstrations of measurement taking process.

- **Palatal transverse width** - measured at the primary canines (cusp tips) and the lingual surface of the 2nd molars (narrowest distance measured at gingival margins):
 - a. Anterior intercanine measured between the primary canines (cusp tips) - Image 2a of Thilander et al. 2009.

[figure not shown]

Figure. Image taken from Figure 2a of Thilander et al. 2009

- b. Posterior intermolar measurement between the lingual surface of the 2nd molars (narrowest distance measured at gingival margins): Bogue index

JOUR. A. M. A.
DEC. 2, 1922

the width of the maxillary arch
determines whether or not there is room for normal
nasal breathing.

Figure. Image taken from Bogue, E.A. 'The Relations of the Dental Arches to Pathologic Affections of the Nasopharynx'. Amer Med. Assoc., Transactions of Section on Dis. of Childhood, 58:110 (1907).

- **Palatal sagittal depth/length** - measured anteriorly from the incisive papilla perpendicularly to a line connecting and posteriorly along the same line perpendicular to the disto-gingival margins of the 2nd molars (at alveolar crests);
 - a. Posterior depth/length: Figure 3 from Thilander et al. 2009

[figure not shown]

Figure. Image taken from Figure 3a of Thilander et al. 2009

(b) Arch Depth

[figure not shown]

Figure. Image taken from Figure 3b of Thilander et al. 2009

- **Palatal vault height:** measured from the center of the line connecting the disto-gingival margins of the 2nd molars (at alveolar crests) down to the contact with the mid-palatal suture.

Palatal Height

Figure. Image taken from Figure 4 of Thilander et al. 2009

- Any changes to patients usual oral routines

C-GASP questionnaire

This survey collects clinical information on the signs and symptoms associated with breathing disturbances.

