 - i. All groups (including control): 30 minutes
- 3. Week 24 (6 months)
 - g. All groups (including control): 1 hour at CCC-SLP and Dentist, total = 2 hours

Treatment timeline

- 1. Initial treatment consults involve educating patients on protocol - occurs 2 weeks after first measurement and successful eligibility screen
 - a. Myo Munchee ONLY group: 15 minutes
 - b. OMT ONLY group: 30 minutes
 - c. Myo Munchee + OMT group: 30 minutes
- 2. Every 2 weeks until week 10 (T10), 8 weeks after initial treatment appointment:
 - a. Myo Munchee ONLY group: 15 minutes
 - b. OMT ONLY group: 30 minutes
 - c. Myo Munchee + OMT group: 30 minutes
- 3. Every 4 weeks after T10 until week 26 (T26):
 - a. Myo Munchee ONLY group: 15 minutes
 - b. OMT ONLY group: 30 minutes
 - c. Myo Munchee + OMT group: 30 minutes

At home timeline

- 1. The exercises prescribed by the CCC-SLP will need to be completed at home outside of therapy appointments
- 2. The weekly and total time commitment over the 6 months
 - a. Myo Munchee ONLY - 6 days/week
 - i. Weekly: 72 minutes/week
 - ii. Total at home time commitment = 31 hours
 - b. OMT ONLY - 6 days/week
 - i. Weekly: 90 minutes OMT exercises.
 - ii. Total at home time commitment = 39 hours
 - c. Myo Munchee and OMT - 6 days/week
 - i. Weekly: 72 minutes Myo Munchee chewing, 90 minutes OMT exercises.
 - 1. Total = 2 hours, 42 minutes
 - ii. Total at home time commitment = 70 hours

Total Time commitment

Enrolling in the study is a 26-week commitment with variation in time commitments for each group.

- 1. Treatment groups
 - a. **Myo Munchee Only:**
 - i. Initial measurement consultation: 1 hour at dentist and CCC-SLP = 2 hours

- ii. T10 and T26 measurement appointments: 1 hour at dentist and CCC-SLP = 4 hours

- iii. Treatment appointments:

- 1. Before T10: 15 minutes every 2 weeks = 1 hour

- 2. After T10: 15 minutes every 4 weeks = 1 hour

- iv. Commitment outside of appointments: Weekly: 72 minutes/week. Total = 31 hours

- v. Total time commitment: approximately **39 hours**

b. Oral Motor Therapy ONLY:

- i. Initial measurement consultation: 1 hour at dentist and CCC-SLP = 2 hours

- ii. T10 and T26 measurement appointments: 1 hour at dentist and CCC-SLP = 4 hours

- iii. Treatment appointments:

- 1. Before T10: 30 minutes every 2 weeks = 2 hours

- 2. After T10: 30 minutes every 4 weeks = 2 hours

- iv. Commitment outside of appointments:

- 1. Oral Motor Therapy: 90 minutes/week. Total = 39 hours

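### Screening criterion 3 is worded to bar outside care for any dental issue, with no exception for routine or urgent dental care; it should be limited to malocclusion and OMD treatment

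*Protocol*

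**What the plan says.** Under Screening Criteria, item 3, the family "Agrees to not seek out other medical treatment for their dental or OMD issues". The sentence does not define a dental issue, has no end date and makes no exception.

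The conditions under study are set out in the inclusion criteria. Inclusion 2 requires at least two "maxillary skeletal-dental malocclusion traits as determined by the measurements below". Inclusion 3 requires at least one of the "identified OMD traits detailed below".

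The arms are the chewing device (A), oral motor exercises (B), both (C) and "Group D: Control, no treatment". The dentist appointments appear in the timelines as measurement appointments.

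For the primary outcomes, palatal width is "measured at the primary canines (cusp tips) and the lingual surface of the 2nd molars". The Dental Measurements list ends with a question on "Any changes to patients usual oral routines", and a footnote to the Measurement and Treatment Timeline asks about changed activities, with gum chewing as its example.

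**The concern.** A ban on competing treatment is ordinary and sensible in a four-arm comparison that includes an untreated control. The difficulty is that the ban is written more widely than that purpose needs. A dental issue in everyday language includes toothache, infection, decay or a broken tooth, and a parent or site coordinator who takes the sentence at face value could conclude that a dentist should not be consulted for these. The participants are 3-5 years old and depend on others to seek care for them.

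There is also a smaller data interest. An extraction, crown or injury at a measured tooth can change a measurement for reasons unrelated to study therapy. If necessary care is expressly allowed and recorded, such a change can be recognised. If families think it is not allowed, it may go unreported.

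**Working it through.** No figure is in dispute, so the check is a reading of the protocol against four questions.

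1. **Is the restriction tied to the entry conditions?** Inclusion 2 and 3 define specific maxillary and OMD traits. Screening 3 does not refer back to them. OMD is named, but the other limb is simply dental.

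2. **Does the protocol use dental to mean malocclusion?** Not consistently. Exclusion 9 lists dental, OMT and orthodontic providers as three kinds, so dental is something apart from orthodontic. Exclusion 10 uses dental of caries. The protocol's own vocabulary therefore does not narrow the sentence.

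3. **Is there an exception elsewhere?** There are three candidates, and none serves.
   - Exclusion 1 tolerates routine follow-up examinations, but only within the entry definition of a healthy child.
   - Exclusion 10 deals with caries at entry and says nothing about decay, pain or injury that arises later.
   - The section on protocol deviations mentions urgent safety measures, but as an example of a deviation and without reference to dental care.

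4. **Does any arm supply the care in question?** Groups A to C receive chewing and/or exercises under the speech-language pathologist. Group D receives nothing. No conventional dental treatment (for decay, pain, infection or injury) is described in any of the four arms.

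**Reach.** Screening 3 applies before allocation, so it covers all 4 x 12 = 48 children alike. Enrolment is described as a 26-week commitment, which is the natural reading of how long the agreement lasts, although the criterion does not say so.

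**Landmarks.** Anterior width uses the primary canine cusp tips and posterior width the second molars. Sagittal depth and vault height are both referred to the second-molar margins. All three primary outcomes therefore depend on the second molars, and width also on the canines. The existing question on changes concerns routines and activities; as worded it does not ask about dental treatment.

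**The case against.** The best defence is the grammar. The word *their* points to issues that the child has at screening, and *other* means other than the study treatment. Exclusion 10 has removed children with caries, and exclusion 2 those with head, neck or jaw trauma. For a child who passes these, the dental issue on record is the malocclusion, and a later toothache is not part of the agreement. This makes the narrow reading the likely intent. It does not put the limit into the sentence, and a condition that families must accept should not rely on such inference.

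It is also fair that families are informed through consent and recruitment material that is not in the copy reviewed, and that a protocol need not describe usual care. The section on data access refers to treating clinicians who have the child under their professional care, so the study dentist may be the child's own. All of this limits the point to the protocol sentence.

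Three stronger inferences are tempting, and the documents do not support them:

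- *That the trial withholds dental care from children.* The protocol does not say this, and the wording families receive is unknown.
- *That the control group is especially exposed.* Groups A to C have treatment visits "Every 2 weeks until week 10 (T10), 8 weeks after initial treatment appointment" and every 4 weeks afterwards, while group D has none. But those are therapist visits, possibly by video. Dentist visits follow the same schedule in all four groups, and the 72-hour reporting rule for adverse events is not tied to visits. The difference measures therapist contact, not access to dental care.
- *That a child taken to a dentist would drop out of the per-protocol analysis*, because "only subjects who did not deviate from the protocols will be included". That presupposes the broad reading, and the detailed rules for that set can properly be left to the SAP, which is not shown.

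**Conclusion.** The point holds as a matter of wording. Screening 3 states a restriction broader than its likely purpose, with no exception for routine or urgent dental care and no arm that provides it. Followed literally, it works against the safety of young children; followed as probably intended, it does no harm. It is not evidence of a flaw in the randomised comparison, since the same condition applies in every arm.

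Its size cannot be given as a number of children. The condition covers all 48, but the protocol gives no rate of dental problems, and the exclusion of caries at entry should lower it. The conclusion assumes that no appendix or family document outside the copy reviewed already makes the exception. If one does, the protocol should be brought into line with it.

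**What to change.** Replace Screening 3 with:

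> *Agrees not to seek treatment outside the study for malocclusion or OMD (orthodontic, oral-appliance, oral-motor or myofunctional treatment, tongue-tie release) until the final study visit. Routine and urgent dental or medical care (e.g. for caries, pain, infection or injury) is always allowed and is recorded.*

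Add to exclusion 9 that it applies at entry and does not restrict such care during the study. Otherwise its unqualified reference to other dental providers would leave the same doubt. Extend the existing question on changes to ask about dental treatment and which teeth were treated. Use the same wording in anything given to families, if it is not already there.

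The cost is a few lines of text and one added item on an existing form. The ban on co-interventions is kept. The one downside is that some of the dental care so allowed may affect a landmark, but it will then be on record.
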